1.0 Objectives

1.1 *Describe the purpose, specific aims, or objectives.*

We propose to study the effect of Acthar® on recovery from cognitive relapses in multiple sclerosis (MS). Cognitive relapses are acute clinical declines in concentration, memory, working memory or increased fatigue. Cognitive relapses may also be detected by the presence on brain MRI of new active supratentorial Gad enhancing lesions. We will use well-validated, objective metrics to evaluate cognitive changes following treatment with a 5-day course of Acthar® over three months in patients showing cognitive relapses in MS. To account for the possible practice effects of cognitive testing over a three-month period, we will compare the results to a matched sample of MS patients who are clinically stable.

1.2 *State the hypotheses to be tested.*

The primary hypothesis of the study is that due to enhanced melanocortin response, Acthar will facilitate recovery from cognitive changes occurring during cognitively focused relapse, and that patients treated with Acthar will return to baseline following treatment.

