3.0 Inclusion and Exclusion Criteria

3.1 Describe the criteria that define who will be included or excluded in your final study sample.

Inclusion Criteria:

- (1) Identification by clinical care provider of new acute (defined by clinician as a symptom of recent origin developing with a time span of 48 hours) cognitive relapse or supratentorial GAD enhancing lesions on MRI with confirmation of cognitive decline.
 - (1a) Confirmation of cognitive decline will be obtained by administering the SDMT as a screening procedure for the study. Participants will qualify if they show a > -3 raw score point change on SDMT (relative to baseline identified to meet criteria #4).
- (2) Males/Females between the ages of 18-65 years who are capable of understanding and complying with the protocol, speak and write fluent English, and have at least a 9th grade education.
- (3) Have a diagnosis of Relapsing Remitting or early Secondary Progressive MS as per revised McDonald's Criteria.
- (4) Valid NP testing in the past 4-5 years
- (5) EDSS of ≤ 7.0
- (6) Have given written informed consent prior to any study-related procedure not part of normal medical care, with the understanding that consent may be withdrawn by the subject at any time without prejudice to his/her future medical care.
- (7) Are capable of performing the requirements of a NP test battery including at least 20/70 near visual acuity by near vision chart, with correction.

Exclusion Criteria:

- (1) Have cognitive deficits caused by concomitant medication usage or other significant neurological/psychological disease e.g. Alzheimer's disease, Parkinson's disease, stroke, transient ischemic attack, Vascular Dementia, Huntington's disease, traumatic brain injury, or chronic CNS infection.
- (2) Have evidence of any other medical cause(s) of cognitive impairment.

University at Buffalo Institutional Review Board (UBIRB)

Office of Research Compliance | Clinical and Translational Research Center Room 5018
[name]
UB Federalwide Assurance ID#: FWA00008824

PROTOCOL TITLE: Effects of adrenocorticotropic hormone (Acthar gel®) on recovery from cognitive relapses in MS.

- (3) Have evidence of current major depression as determined by a positive BDI-FS and clinician interview.
- (4) Clear new physical signs or symptoms that are referable to the spinal cord, brainstem, or optic nerve.
- (5) Evidence on MRI of new lesions in the brainstem, spinal cord, or optic nerve.

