8.0 Study Endpoints

8.1 *Describe the primary and secondary study endpoints.*

Primary measures will include: Symbol Digit Modalities Test,¹⁴ Brief Visualspatial Memory Test- Revised,¹⁵ Paced Auditory Serial Addition Test,¹⁶ and the Multiple Sclerosis Functional Composite (MSFC).²³ These tests are some of the strongest indicators of clinically relevant cognitive change available in MS.

The Symbol Digit Modalities Test (SDMT) will be used to measure visual processing speed. This test presents a stimulus key of numbers paired with abstract symbols at the top of a page. Participants scan the page below the key which has rows of symbols without the paired numbers. The task is to generate the associated numbers orally as fast as possible. We will employ the Rao oral adaptation²⁴ of the SDMT as the oral presentation has been deemed most appropriate for use with a potentially motor impaired population.¹²

University at Buffalo Institutional Review Board (UBIRB)

Office of Research Compliance | Clinical and Translational Research Center Room 5018
[name]
UB Federalwide Assurance ID#: FWA00008824

PROTOCOL TITLE: Effects of adrenocorticotropic hormone (Acthar gel®) on recovery from cognitive relapses in MS.

The Paced Auditory Serial Addition Test (PASAT)²⁵ 3 sec interval version will be used as an indicator of working memory performance. The PASAT is an auditory task in which subjects are exposed to single digit numbers voiced every three seconds. After each number presentation, the subject's task is to respond with the sum of the last two digits presented. As each new number is presented, the subject must recall the previous digit, add them together, and respond before the next number is presented.

The Multiple Sclerosis Functional Composite (MSFC)²³ is a composite measure incorporating aspects of cognition, walking speed and manual dexterity. The 25-foot walk, 9-hole peg test, and PASAT 3-sec (described above) are normalized based on an established normative sample and an overall composite z- score is then determined. This composite is frequently used as a primary outcome in clinical trials as it covers three major domains of function potentially impaired in MS.

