9.0 Procedures Involved

University at Buffalo Institutional Review Board (UBIRB)

Office of Research Compliance | Clinical and Translational Research Center Room 5018
[name]
UB Federalwide Assurance ID#: FWA00008824

PROTOCOL TITLE: Effects of adrenocorticotropic hormone (Acthar gel®) on recovery from cognitive relapses in MS.

9.1 Describe and explain the study design.

9.2 Provide a description of all research procedures being performed and when they are performed, including procedures being performed to monitor subjects for safety or minimize risks.

Initial referral will be initiated by treating physicians. Following confirmation of the subject's relapse status and/or the presence of new supratentorial GAD enhancing lesions, patients deemed eligible for Acthar treatment will be screened for symptoms of infection and evaluated by their treating physician. If the patient agrees, the clinician will contact the research coordinator with the referral.

At this time, all participants will undergo study eligibility screening and consent by a Clinical Research Project Coordinator. The project coordinator or a designated member of the research team will meet, in person, with the participant to discuss the study objectives and procedures, so that he/she can make an informed decision regarding voluntary study participation. Participants will have an opportunity to ask questions regarding the study, procedures, etc. At this time, the study coordinator will administer the SDMT to the relapsing patient. The study coordinator will give this score to another study personnel. At this time the other

University at Buffalo Institutional Review Board (UBIRB)

Office of Research Compliance | Clinical and Translational Research Center Room 5018
[name]
UB Federalwide Assurance ID#: FWA00008824

PROTOCOL TITLE: Effects of adrenocorticotrophic hormone (Acthar gel®) on recovery from cognitive relapses in MS.

study personnel will check the patient's baseline SDMT score. If this score is less than or equal to a 3 point decline, the patient will be deemed eligible for the study. Participants who choose to enroll in the study will then be asked to sign and date a consent form in front of the Study Coordinator.

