11.0 Data Management

11.1 Describe the data analysis plan, including any statistical procedures.

Data will be processed by trained research assistants blind to study hypotheses. Analysis will be conducted using SPSS 22.0. Analysis strategy will be repeated measures analysis of variance where baseline, day 0 and day 90 scores are compared. Analysis of variance will be used

University at Buffalo Institutional Review Board (UBIRB)

Office of Research Compliance | Clinical and Translational Research Center Room 5018
[name]
UB Federalwide Assurance ID#: FWA00008824

PROTOCOL TITLE: Effects of adrenocorticotropic hormone (Acthar gel®) on recovery from cognitive relapses in MS.

to compare the magnitude of change between day 0 and 90 between the MS patients treated with Acthar and the previously collected controls. Analysis of variance will also be used to compare the magnitude of cognitive recovery after corticosteroid treatment to that after Acthar treatment.

The difference between the means at Day 0 and Day 90 will be used to calculate Cohen's d for each group. To facilitate analysis, all data will be normalized using a large previously published control sample.¹³ All tests will be performed based on an alpha of 0.05. Net effect sizes removing estimated practice effects will be calculated using Cohen's d.

11.2 Provide a power analysis.

The selection of 30 as the target enrollment is based on the previously completed study of 25 relapsing and 25 stable MS patients. Five additional patients are planned in order to increase the power of subsequent analyses. A power analysis based on the observed effect of corticosteroids in the relapsing group of $d = .56$ with 30 participants will be powered $>85\%$ to detect effects of a moderate magnitude from Acthar.

11.3 Describe the steps that will be taken to secure the data (e.g., training, authorization of access, password protection, encryption, physical controls, certificates of confidentiality, and separation of identifiers and data) during storage, use, and transmission.

All clinical and neurometric assessments will be conducted under the supervision of the PI. All members of research team will complete relevant training programs and courses, including but not limited to: HIPAA, CITI and GRP.

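### Decline is confirmed on the SDMT only, so recovery on BVMT-R, PASAT and MSFC cannot be interpreted unless a loss on each is shown

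*Combined protocol and SAP*

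**What the plan says.** - **Target condition (section 1.1):** "Cognitive relapses are acute clinical declines in concentration, memory, working memory or increased fatigue". The domains are alternatives, so a relapse need not involve memory or working memory.
- **Entry check (section 3.1, criterion 1a):** "Confirmation of cognitive decline will be obtained by administering the SDMT as a screening procedure for the study". Section 9.2 applies the same single test before enrolment.
- **Threshold:** criterion (1a) reads "Participants will qualify if they show a > -3 raw score point change on SDMT (relative to baseline identified to meet criteria #4", while section 9.2 reads "If this score is less than or equal to a 3 point decline, the patient will be deemed eligible for the study".
- **Prior testing (criterion 4):** "Valid NP testing in the past 4-5 years". The tests are not named.
- **Primary measures (section 8.1):** SDMT, BVMT-R, PASAT and MSFC, with no order among them. The SDMT is assigned to visual processing speed and the BVMT-R to episodic memory. The PASAT "will be used as an indicator of working memory performance". The MSFC combines the PASAT with a timed walk and a peg test.
- **Hypothesis (section 1.2):** recovery, and return to baseline after treatment.
- **Analysis (section 11.1):** repeated measures ANOVA over baseline, day 0 and day 90. The comparison with controls and Cohen's d both use only the change from day 0 to day 90.
- **Power (section 11.2):** above 85% with 30 participants and d = .56 "to detect effects of a moderate magnitude from Acthar". The measure behind d is not named.

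**The concern.** Entry is verified in one domain, while recovery is to be claimed in several. Three consequences follow.

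1. A null day 0 to day 90 result on BVMT-R, PASAT or MSFC cannot separate a treatment that failed from a group with little to recover.
2. For the return-to-baseline hypothesis the error runs the other way. Patients who never declined on a test are already at baseline and count as returned.
3. A positive result would be reported for cognitive relapses in general, although the patients studied were confirmed on processing speed only.

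**Working it through.** **1. The plan's power figure.** Inputs from sections 11.1 and 11.2: d = .56, n = 30, alpha .05. Two-sided testing is assumed, as is a d in units of the SD of change; the plan states neither.
- Within-group, normal approximation: Φ(d√n − 1.960) = Φ(0.56 × 5.477 − 1.960) = Φ(1.107) = 86.6%. This reproduces the stated figure. The paired t version gives 84.2%.
- Change in 30 treated patients against 30 controls (section 23): Φ(0.56 × √15 − 1.960) = Φ(0.209) = 58.3%; t version 56.9%.

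So the stated power matches a within-group comparison on one unnamed measure. If d was scaled on raw scores, the result depends on the day 0 to day 90 correlation. Assumed correlations of .5 to .8 give 84.2% to 99.7% within-group and 56.9% to 92.1% against controls (t versions). The scaling should therefore be stated too.

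**2. Direction of the two errors.** Take one test. Let a share f of patients have a mean true loss L and recover a mean amount R by day 90. The rest have no loss. Leave practice effects aside.
- Mean day 0 to day 90 recovery = f × R, which shrinks towards zero as f falls.
- Mean shortfall from prior baseline at day 90 = f × (L − R). This also shrinks towards zero as f falls, even when R = 0.

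A small f therefore makes recovery look absent and return to baseline look complete at the same time. Only the group loss from prior baseline to day 0, f × L, tells these situations apart. The documents give none of f, L and R for any test.

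**3. The MSFC.** It inherits the PASAT problem. Its other two parts measure walking and dexterity, while exclusion (4) removes patients with clear new physical signs referable to the spinal cord, brainstem or optic nerve. A relapse-related loss on those parts is not required either.

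**4. Why the SDMT cannot simply carry the conclusion.** It is the selection test. Suppose there is no true change, entry needs a fall of at least 3 points (one reading of the threshold), the SDMT has SD σ and retest reliability r, and errors are independent. With σ_D = σ√(2(1 − r)) and c = 3/σ_D, the expected rise from the screening score to day 90 is ½ σ_D φ(c)/(1 − Φ(c)).
- σ = 10, r = .9: σ_D = 4.47, rise 2.8 points.
- σ = 13, r = .7: σ_D = 10.07, rise 5.0 points.

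Both σ and r are assumptions. With the second SDMT of section 9.2 as day 0, simulation gives an expected rise of about zero. If both SDMTs fall at the same visit and share that day's error, some rise remains. By symmetry the prior baseline is too high by the same 2.8 to 5.0 points, so part of any SDMT loss shown is built in by selection.

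**The case against.** Confirming a relapse on one sensitive test and measuring several domains is a legitimate design. A clinician or an MRI finding also gates entry. Section 11.1 already lists baseline separately from day 0, and criterion (1a) ties baseline to the prior testing, so the ANOVA covers loss as well as recovery.

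Much of this stands. The data for the remedy are largely planned. What is missing is a rule linking a recovery claim to a shown loss, and any assurance that prior testing included each measure. Neither Cohen's d nor the comparison with controls uses the prior score. Neither the clinical nor the MRI route requires a loss on BVMT-R, PASAT or MSFC.

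Stronger readings that the documents do not support:
- **A specific loss of power.** A reader might multiply .56 by an assumed share: with half the patients affected, d = .28 and power is about 32% (paired t, n = 30). The share is invented. Section 11.2 describes .56 as the effect in the whole relapsing group, so patients without a loss may already be averaged into it.
- **Zero change in patients without a loss.** Section 2.2 credits melanocortins with improving attention, memory and learning without requiring a deficit, and practice gains are expected. Losses may also overlap across tests.
- **Every memory-only or fatigue-only relapse fails screening.** This depends on the threshold. Read literally, the section 9.2 wording admits patients with little or no SDMT fall, and the problem would then reach the SDMT as well.
- **The power figure belongs to the SDMT.** Section 11.2 does not say so.

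**Conclusion.** The mismatch is real. Decline is objectively confirmed on the SDMT alone, while BVMT-R, PASAT and MSFC are also primary measures of recovery. As planned, a null on those three is ambiguous, and an apparent return to baseline may reflect patients who never declined. The direction of both errors holds whenever some patients have no loss on the test and therefore no relapse-related recovery to show. The size cannot be stated, because the share with a loss and the measure behind d = .56 are not given. The case for change is that it is cheap and alters what the trial may conclude; it does not rest on a calculated loss of power.

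**What to change.** - **Sections 3.1 and 9.2:** reconcile the two statements of the SDMT threshold first.
- **Sections 1.1 and 1.2, and the conclusion:** state that the population is relapses with SDMT-confirmed decline.
- **Section 11.1:** for each primary measure, report the loss from prior baseline to day 0 (where prior testing included that test) beside the day 0 to day 90 change and the control change. Draw a recovery or return-to-baseline conclusion only where a group loss is shown, by a criterion fixed in advance. Otherwise report that there was no loss to recover.
- **SDMT:** use the second SDMT of section 9.2 as day 0, not the screening score. Do not rest the recovery conclusion on the SDMT alone without stating that it is the selection test and open to regression to the mean.
- **Section 11.2:** name the measure and scaling behind d = .56, and limit the power statement to that measure and to the within-group comparison.

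Cost: no new patients, visits or tests. The claim is narrower. Measures without a shown loss, or missing from prior testing, may end with no recovery conclusion.

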23.0 Local Number of Subjects

23.1 Indicate the total number of subjects to be accrued locally.

University at Buffalo Institutional Review Board (UBIRB)

Office of Research Compliance | Clinical and Translational Research Center Room 5018
[name]
UB Federalwide Assurance ID#: FWA00008824

PROTOCOL TITLE: Effects of adrenocorticotrophic hormone (Acthar gel®) on recovery from cognitive relapses in MS.

We will enroll 30 relapsing-remitting MS patients and 30 stable MS patients.

23.2 If applicable, distinguish between the number of subjects who are expected to be enrolled and screened, and the number of subjects needed to complete the research procedures (i.e., numbers of subjects excluding screen failures.)

During routine clinic appointments, cognitively relapsing patients will be assessed (by the treating clinician) for suitability for the study. Subjects who agree to participate and pass screening requirements will be enrolled in the study. Thirty relapsing MS patients and 30 stable MS controls will be enrolled.

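### The SDMT entry rule in criterion (1a) points the wrong way as written, section 9.2 can be read in two opposite directions, and even as intended the two disagree on a loss of exactly 3 points

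*Combined protocol and SAP*

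**What the plan says.** Section 3.1, criterion (1a), gives the purpose of the test first: "Confirmation of cognitive decline will be obtained by administering the SDMT as a screening procedure for the study". It then sets the threshold: "Participants will qualify if they show a > -3 raw score point change on SDMT (relative to baseline identified to meet criteria #4". The baseline is the earlier neuropsychological testing required by criterion (4).

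Section 9.2 describes the same check as it is carried out. The coordinator administers the SDMT, and then: "The study coordinator will give this score to another study personnel". That second person looks up the earlier result ("study personnel will check the patient's baseline SDMT score"), and the decision rule follows: "If this score is less than or equal to a 3 point decline, the patient will be deemed eligible for the study".

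Two other sections bear on the weight of this rule. Section 8.1 lists the SDMT as an endpoint: "Primary measures will include: Symbol Digit Modalities Test". Section 23.1 gives the sample size: "We will enroll 30 relapsing-remitting MS patients and 30 stable MS patients".

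**The concern.** The SDMT is a speeded task (section 8.1: "The task is to generate the associated numbers orally as fast as possible"), so more responses is better and a decline is a negative change. A screen meant to confirm decline should admit patients whose change is sufficiently negative. As a signed inequality, the rule in (1a) does the reverse.

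Section 9.2 does not repair this. It never defines a difference score, and its reference to a score has no clear antecedent: the screening score and the baseline score are both named just before it. The sentence can mean that the decline is no larger than 3 points, or that the screening score lies at least 3 points below baseline. Those readings admit almost entirely different patients.

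The SDMT cut is the only numerical confirmation of cognitive decline among the entry criteria. Without one rule, a patient at the threshold can be accepted or refused depending on which section staff follow, and a later audit cannot say with confidence whether that enrolment was a protocol deviation.

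**Working it through.** **Inputs.** Change is defined here as screening SDMT minus criterion (4) baseline SDMT, in raw points, which are whole numbers. The comparator is strict in (1a) and includes 3 in section 9.2. The direction of scoring comes from section 8.1. The plan states no figure that could be reproduced on this point, so the check is an enumeration of the possible readings.

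**Step 1: four readings.**

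- (1a) literal: change > -3.
- (1a) intended: loss > 3, so change ≤ -4.
- 9.2 literal: size of decline ≤ 3, so change ≥ -3.
- 9.2 intended: screening score at or below baseline minus 3, so change ≤ -3.

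**Step 2: eligibility by change score.**

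| Change | (1a) literal | 9.2 literal | (1a) intended | 9.2 intended |
|---|---|---|---|---|
| Gain, 0, -1 or -2 | Yes | Yes | No | No |
| -3 | No | Yes | No | Yes |
| -4 or lower | No | No | Yes | Yes |

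No change score is eligible under all four readings. (1a) literal and 9.2 intended are exact complements, as are (1a) intended and 9.2 literal. Literal against literal, the sections differ only at -3. Intended against intended, they also differ only at -3. If 9.2 literal is taken to require some decline (1 to 3 points only), it also parts from (1a) literal at 0 and at every gain.

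**Step 3: how many patients could sit at the boundary.** The document gives no distribution of SDMT change in relapse, so this step is illustrative. Assume a normal change with mean m and SD s, rounded to whole points, and 30 patients enrolled under the 9.2 intended rule.

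- P(change = -3) = Φ((-2.5 - m)/s) - Φ((-3.5 - m)/s)
- P(change ≤ -3) = Φ((-2.5 - m)/s)
- Share at the boundary = P(change = -3) / P(change ≤ -3)

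For m = -4, s = 5: (Φ(0.3) - Φ(0.1)) / Φ(0.3) = 0.0781 / 0.6179 = 12.6%, and 30 × 0.126 = 3.8 patients.

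For m = -4, s = 7: 0.0564 / 0.5848 = 9.6%, or 2.9 patients.

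| Mean change | SD 5 | SD 7 |
|---|---|---|
| -2 | 17.0% (5.1 of 30) | 12.0% (3.6 of 30) |
| -4 | 12.6% (3.8 of 30) | 9.6% (2.9 of 30) |
| -6 | 8.8% (2.6 of 30) | 7.5% (2.3 of 30) |

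The share depends on the values assumed. The same formula gives 28.9% (8.7 of 30) at mean -2, SD 3, and 5.6% (1.7 of 30) at mean -8, SD 5.

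**Step 4: effect on the selected group.** At mean -4, moving the cut from change ≤ -3 to change ≤ -4 raises the mean loss from baseline to screening from 7.10 to 7.69 points at SD 5 (difference 0.59) and from 8.67 to 9.28 at SD 7 (difference 0.61).

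**The case against.** The strongest reply is that the intent is plain. The sentence before the threshold in (1a) says the test confirms decline, the minus sign marks a loss, and a sensible reader takes the rule as a drop of more than 3 points. A clinician has also already identified the relapse or enhancing lesion, and judged the patient eligible for Acthar, before the SDMT check in section 9.2. This largely stands: the wording would not by itself bring in patients with no identified relapse, and staff would probably apply the intended direction. The minus sign itself is not the error; the direction of the inequality is.

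One could add that section 9.2 describes a single sequential check, not two competing decisions, and that section 3.1, as the list of entry criteria, should govern. That is a reasonable convention, but no precedence clause is written, and section 9.2 is the text staff follow when they make the comparison. The conflict at -3 therefore remains.

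Two further objections stand as limits. The boundary figures rest on assumed distributions and should not carry the argument. And the shift in step 4 concerns loss from the historical baseline, whereas section 11.1 compares change from day 0 to day 90 between groups, and the SDMT is repeated in the full assessment after screening. No effect on the between-group result has been calculated here.

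**Conclusion.** The point holds. Criterion (1a), read as a signed change, contradicts its own stated purpose. Section 9.2 supports two opposite readings. With both read as intended, a loss of exactly 3 points is eligible under section 9.2 and ineligible under (1a), and no other section resolves it. These conclusions come from the wording alone and need no assumption beyond higher SDMT scores being better.

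The practical harm is mainly at the boundary. On the illustrative grid in the working (normal change, mean -2 to -6, SD 5 to 7) it concerns about 2.3 to 5.1 patients in a treated group of 30; other assumptions give more or fewer. This is a drafting error in an eligibility rule and should be fixed. It does not make the trial invalid.

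**What to change.** Define change once as screening SDMT minus the criterion (4) baseline SDMT, in raw points. Put the same signed inequality, word for word, in section 3.1 (1a) and section 9.2, and name the score being compared in section 9.2. The sponsor and investigator should state whether a loss of exactly 3 points qualifies; this review does not choose.

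The cost is a one-line amendment in two sections. If patients are already enrolled, list each one's screening score, baseline score, change and the rule it met, so that any enrolment at exactly -3 is visible and can be classified.

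### The earlier test that anchors the 3-point SDMT entry rule is not defined, and it is looked up with the screening score already in hand

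*Combined protocol and SAP*

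**What the plan says.** - Section 3.1(1a), the entry rule: "Participants will qualify if they show a > -3 raw score point change on SDMT (relative to baseline identified to meet criteria #4".
- Section 3.1(4), the whole definition of the comparator that (1a) describes as "relative to baseline identified to meet criteria #4": "Valid NP testing in the past 4-5 years". The word valid is not defined, and the window is itself a range.
- Section 9.2, the order of steps. The coordinator gives the screening SDMT, then: "The study coordinator will give this score to another study personnel". After that the other "study personnel will check the patient's baseline SDMT score".
- Section 9.2, the decision: "If this score is less than or equal to a 3 point decline, the patient will be deemed eligible for the study".
- Section 8.1, the SDMT version: "We will employ the Rao oral adaptation". This governs the study's own testing. The reason given is that patients may be motor impaired.
- Section 11.1, use in the analysis: "Analysis strategy will be repeated measures analysis of variance where baseline, day 0 and day 90 scores are compared".
- Section 1.2 makes return to baseline after treatment part of the primary hypothesis.

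**The concern.** One historical score does three jobs: it decides entry, it is the first level of the three-time-point ANOVA, and it is the natural target for return to baseline. The protocol leaves open which score that is.

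Two gaps need separating. The first arises only when a patient has two or more eligible earlier sessions: no rule picks one, and the person retrieving the score already knows the screening result. The second can arise even with a single session. Criterion (4) as written accepts a test taken during an earlier relapse, or one using a different SDMT version, although raw points are compared. Section 8.1's reason for the oral form implies that written and oral scores are not interchangeable in patients with motor impairment.

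A comparator that is too high admits patients with no acute loss and sets a recovery target they may never reach. One that is too low keeps out real relapses and makes the target easy to reach. With a target of 30 relapsing patients, a few such cases would matter.

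**Working it through.** The plan gives no figure on this point. Its only design calculation, power above 85% in section 11.2, reproduces as a paired normal approximation, Φ(0.56·√30 − 1.96) = Φ(1.107) = 86.6%. It does not depend on the comparator.

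**Inputs.** The threshold of 3 raw points comes from sections 3.1(1a) and 9.2. The documents give no SDMT error SD and no number of earlier tests per patient. Assumed here: error SD s of 2 to 5 points at every session, whole-point scores, no practice gain, and one or two eligible earlier tests.

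**One fixed comparator, no true change.** The difference of two scores has SD s√2. A fall of more than 3 means 4 or more whole points, so the chance is about 1 − Φ(3.5/(s√2)).
- s = 2: 1 − Φ(3.5/2.83) = 1 − Φ(1.24) = 11%
- s = 5: 1 − Φ(3.5/7.07) = 1 − Φ(0.495) = 31%

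**Two eligible tests, no true change** (simulation, 400,000 draws, fall of more than 3):

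| s | One fixed test | Higher of two | Lower of two | The two disagree |
|---|---|---|---|---|
| 2 | 10.9% | 18.1% | 3.7% | 14.4% |
| 3 | 20.6% | 32.1% | 9.1% | 23.0% |
| 4 | 26.7% | 40.2% | 13.3% | 26.9% |
| 5 | 31.1% | 45.7% | 16.5% | 29.1% |

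With a true 3-point fall, two eligible tests disagree in about 33% of patients across this range of s. Always taking the higher of two raises the comparator by s/√π = 0.564·s on average, that is 1.1 points (s = 2) to 2.8 points (s = 5).

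**Threshold wording.** Taken as requiring a fall, the two sections leave unclear whether exactly 3 points qualifies. Read literally, either could even admit small falls. Counting a fall of 3 moves the one-test column from 10.9% to 18.9% at s = 2 and from 31.1% to 36.3% at s = 5.

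**A comparator that is too low.** Take a true acute loss of 6 points, a continuous score, a fall of 3 or more, an SD of differences D of 4 to 6, and a comparator c points too low. The chance of qualifying is Φ((6 − c − 3)/D).
- c = 0: Φ(3/4) = 77% to Φ(3/6) = 69%
- c = 1: Φ(2/4) = 69% to Φ(2/6) = 63%
- c = 4: Φ(−1/4) = 40% to Φ(−1/6) = 43%

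The documents support no particular value of c.

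**The case against.** The strongest reply is that the text describes a lookup, not a choice. Section 3.1(1a) speaks of one identified baseline and section 9.2 of checking one score. Tester and checker are already different people, apparently so that the tester scores without knowing the comparator. Subjects come only from this clinic (section 22.2), which has its own lead neuropsychologist (section 20.1), so earlier tests may well be oral and taken when stable.

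Much of this stands. A reader might infer that staff select a comparator to fit the screening score; no passage says so. Separating the two roles is a real safeguard, but it protects the scoring of the screening test. It does not protect retrieval of the comparator, because the checker holds the screening score at that moment. Careful staff would still need a rule when two sessions exist. If valid is meant to exclude relapse testing or other versions, the protocol does not say so.

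The percentages are also open to challenge. They ignore practice gain: with an assumed gain of 2 points, a continuous score, a fall of 3 or more and D of 4 to 6, the one-test rate is 1 − Φ(5/4) = 11% to 1 − Φ(5/6) = 20%. Nor are they rates of wrong enrolment, because criterion (1) first requires a clinician-identified relapse or an enhancing lesion. Both points stand.

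**Conclusion.** The gap is real, and its reach is limited. The comparator is undefined as to session, SDMT version and disease state, and section 9.2 leaves its retrieval unblinded to the screening result. This matters for patients with several eligible tests, or whose only test was taken in a relapse or in another version; the documents do not say how many there are.

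The effect falls on entry, on the three-time-point ANOVA and on the return-to-baseline reading. A reader might infer that the main treatment results are distorted directly. That is not supported: the comparison with controls and Cohen's d in section 11.1 use day 0 and day 90, so they are touched only through who is enrolled. Section 9.2 also repeats the SDMT at the full baseline assessment, so the screening score need not be the day 0 score.

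Nor do the documents support a claim that the gap favours Acthar. A high comparator works against the recovery hypothesis and a low one works for it, so no net direction is shown.

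The size, a pass rate of 4% to 17% against 18% to 46% in unchanged patients according to which of two tests is used, rests on the assumed error SD, on two eligible tests, and on always taking the lower or the higher. It shows that the rule is sensitive to the comparator, not that harm has occurred. The change should be made because it protects an important score at little cost.

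**What to change.** - **Section 3.1(4):** define the comparator as the most recent valid session before relapse onset, taken outside a known relapse and including the oral SDMT.
- **Section 9.2:** have the second staff member record that score before being given the screening SDMT score. Keep the existing separation of tester and checker.
- **Sections 3.1(1a) and 9.2:** reconcile the two threshold wordings into one rule that states whether a fall of exactly 3 points qualifies.
- **Section 11.1:** use earlier BVMT-R and PASAT scores in the three-time-point analysis where they exist. Do not make them an entry condition, which would narrow eligibility further.

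The cost is protocol wording and the order of one lookup, with no new visit or test. Some patients whose only earlier test was in a relapse or in another version would become ineligible. Their number is unknown, and losing them may slow the 48-month enrolment planned in section 7.2.
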